4.2 Intervention

A variety of factors that could potentially predict clinical response to the POLAR regimen will be investigated in peripheral blood and in tumor specimens taken from all participants pretreatment (screening phase), on-treatment, and at the time of disease progression, as outlined in the Treatment and Biospecimen Schema in Figure 1. Data from these investigations will be evaluated for associations with treatment response to POLAR, survival (OS, PFS), and safety (AE).

Research Tissue Collection

All participants will undergo a pre-treatment research biopsy and cfDNA at baseline and during treatment. (Figure 1.) All patients will receive the combination of pembrolizumab 200 mg IV

6

POLAR: a phase 2 trial for pembrolizumab and olaparib maintenance for metastatic PDAC and HRD and/or Exceptional Response to Platinum – Ver. 5/3/2020

every 3 week and olaparib 300 mg twice day orally daily (POLAR) as maintenance therapy. After the first 6 months (9 cycles), on C10D1 Pembrolizumab 400 mg IV every 6 week plus olaparib 300 mg twice a day orally will be continued. At the discretion of the treating investigator, Pembrolizumab 400 mg IV every 6 weeks may begin earlier or Pembrolizumab 200 mg IV every 3 weeks may be continued after C10D1. An on-treatment biopsy (on the 6th- 9th week) and post-progression (before initiation of further therapy) will be obtained where feasible. Biopsies are mandated by protocol baseline and on treatment and at the time of progression except in the setting that there is no disease site that can be safely assessed for biopsy or other clinically relevant safety reason. If tissue acquisition is limited due to availability, available tissues will be prioritized in the following order.

- 1) FFPE (WES, multiplex immunohistochemistry)
- 2) Fresh tissue for single cell analysis with 10-20% cut for organoid culture
- 3) Fresh tissue for single cell analysis
- 4) Fresh frozen for archival

Patients will be presented at multidisciplinary tumor board for discussion related to biopsy safety and site choice were needed. Selected patients with disconcordant and heterogenous response can include up to three different sites for tissue sampling as long as deemed safe.

Research Blood Collection

Peripheral blood mononuclear cells, buffy coat, and plasma will be collected. Circulating tumor DNA on these patients identified as responders and resistant patients will be compared.

Please refer to Section 9 PRE-TREATMENT/INTERVENTION PLAN and 10 TREATMENT/INTERVENTION PLAN.

Samples collected at MSK will be processed and subsequently stored in liquid nitrogen at the Rubenstein M. David Center for Pancreatic Cancer Research at MSK, located on the 6th floor of the MSKCC Mortimer B. Zuckerman Research Center, [name].

All samples will be labeled with the unique subject study identification number provided at registration, sample time point, and the date of the specimen.

Please see Appendix 3. Biomarker Management Plan (BMP) for further details on correlative sample collection details, timepoints, and processing locations.

4.3 Biomarker Assessments

The goal of correlative research: To describe the immunogenomic changes in PDAC when treated with POLAR. Patients' tumor biopsies and peripheral blood from baseline, on-treatment, and at disease progression, will be collected. Novel HRD signature and platinum-sensitivity signatures will be developed and additional immunotherapy targets will be evaluated using single-cell RNAseq technique and single-cell TCRseq, protein expression in bulk as well as single-cell analysis in select cases. Biopsies will be multiple core biopsies (where feasible) and normal adjacent tissue for comparison and biopsies from different lesions at progression will be

POLAR: a phase 2 trial for pembrolizumab and olaparib maintenance for metastatic PDAC and HRD and/or Exceptional Response to Platinum – Ver. 5/3/2020

1 7

highly encouraged in appropriate clinical setting to generate organoids and intertumoral heterogeneity will be described.

Exploratory Objective 1: To describe different genomic and transcriptomic signatures among different HRD and platinum sensitivity cohorts which associates with sensitivity and resistant to POLAR regimen. Several HRD genetic mutational signatures (zygosity, genomic loss of heterozygosity [gLOH], large-scale state transition [LST], telomeric allelic imbalance [TAI], and Signature 3) will be analyzed at baseline in each subgroup (Cohort A, B, and C) will be evaluated. Also, novel genetic signature development will be explored. [name] lab and [name] lab have expertise in genome analysis and will undertake this plan collaboratively.

Exploratory Objective 2: To describe and compare immunologic significance of POLAR treatment in each cohort. The neoantigen induction and the correlation of immunogenic tumor microenvironment (TME) and putative immunomodulatory targets from each cohort will be described. Different neoantigen algorithmic methods, TME and HRD signatures will be described. Innate and adaptive immunity via Stimulator of Interferon Genes (STING, STING/TBK1/IRF3) pathway, immunogenic cell death (ICD), DNA damage as well as the functional assay of PAR, r-H2AX, and RAD51C will be described ⁴⁹. Different immune cell profiling and cytokine analyses from tumor and peripheral blood will be described. Their subtype proportions and T cell receptor clonality change will be explored before and after the treatment and among subgroups. [name] lab has the expertise in neoantigen and immunologic analysis and will undertake this plan collaboratively.

Immunogenic cell death (ICD), innate and adaptive immunity landscape: DNA damage, STING pathway (cGAS, STING, p-TBK1, IRF3), damage-associated molecular pattern (DAMP), immunogenic cell death, CARL, ATP, HMGB1, profiling and functional assays of immune cells (NK cell, memory, effector T cells, dendritic cells, macrophages, myeloid-derived suppressor cells, regulatory T cells) will be evaluated from tumor infiltrates and associated with peripheral blood tumor. TCR Vb clonality at baseline, ontreatment, and on-progression will be described ⁵³.

Tumor microenvironment (TME) evaluation: Cytokines (IFN-r, TNF-a, TGF-b, IL-6, 10), transcriptomic signatures, multispectral immunohistochemistry (e.g. coreceptors including PD-L1, A2AR, CD40, CD73, CD11b, CD68, CD103, TIGIT, VISTA) and immunofluorescent staining for coreceptors and different tumor immune infiltrates, stroma, and normal adjacent tissue will be evaluated. In limited exceptional clinical cases, single cell RNA sequencing will be performed.

Exploratory Objective 3: To evaluate the role of clonal evolution in spatiotemporal heterogeneity influencing the clinical outcome of HRD in patients with metastatic PDAC when treated with POLAR, circulating tumor DNA (ctDNA) and multiple longitudinal tumor biopsies of selected patients will be described to for potential resistance mechanism. [name] lab has the expertise in single-cell analysis technique and will undertake this plan collaboratively.

Exploratory Objective 4: To bank a large biorepository of organoids for patients with HRD. In select patients with viable organoids available from IRB# 15-149 prior to enrollment to POLAR trial, we will concurrently evaluate the response of organoid to POLAR in real time as participants are treated in parallel. [name] lab at Rubenstein Center for Pancreatic Cancer Research has extensive expertise in this field and will undertake this plan. We will collect fresh tissue for organoid development if available for biomarker and resistance studies.

5.0 THERAPEUTIC/DIAGNOSTIC AGENTS & NON-THERAPEUTIC ASSESSMENTS

Both pembrolizumab and olaparib will be supplied for all patients in the trial.

5.1 PEMBROLIZUMAB:

Active Ingredients, pharmacological class, dose formulation, storage:

Pembrolizumab is a potent humanized immunoglobulin G4 (IgG4) monoclonal antibody (mAb) with high specificity of binding to the programmed cell death 1 (PD-1) receptor, thus inhibiting its interaction with programmed cell death ligand 1 (PD-L1) and programmed cell death ligand 2 (PD-L2).

Pembrolizumab Solution for Infusion 100 mg/vial is a liquid DP (manufactured using the fully formulated DS with L-histidine as a buffering agent, polysorbate 80 as a surfactant, and sucrose as a stabilizer/tonicity modifier), and Water for Injection as Solvent). The DP is stored under refrigerated conditions (2°C to 8°C). The liquid is intended for IV administration. The DP is diluted with 0.9% sodium chloride injection, USP (normal saline) or 5% dextrose injection, USP (5% dextrose) to 1-10 mg/mL before intravenous (IV) administration through an infusion filter. Liquid DP is compatible with the IV bag and infusion-line materials. Reconstituted vials should be used immediately to prepare the infusion solution in the IV bag, and the infusion solution should be administered immediately. Do not freeze the diluted solution. If the diluted pembrolizumab solution is not used immediately, it may be stored for no more than 24 hours at 2°C to 8°C. This 24-hour total hold from reconstitution may include up to 6 hours at room temperature (at or below 25°C). Any additional hold time must be at 2°C to 8°C. If refrigerated, the vials and/or intravenous bags must be allowed to come to room temperature before use. The recommended dose of pembrolizumab in adults is either 200 mg Q3W or 400 mg Q6W administered as intravenous infusion over 30 minutes. The recommended dose of pembrolizumab in pediatric patients is 2 mg/kg (up to a maximum of 200 mg), administered as an IV infusion over 30 minutes Q3W. See prescribing information for specific dosing approved in each country.

The planned dose of pembrolizumab for this study is 200 mg every 3 weeks (Q3W). After the first 6 months (9 cycles), on C10D1 Pembrolizumab 400 mg IV every 6 week will be continued. Based on the totality of data generated in the Keytruda development program, 200 mg Q3W is

MSK IRB#: 20-481 A(11), Approval Date: 11-Jun-2024

POLAR: a phase 2 trial for pembrolizumab and olaparib maintenance for metastatic PDAC and HRD and/or Exceptional Response to Platinum – Ver. 5/3/2020

1

the appropriate dose of pembrolizumab for adults across all indications and regardless of tumor type.

For pharmacological class, please refer to Investigator's Brochure.

5.2 OLAPARIB:

Olaparib (AZD2281, KU-0059436) is a potent inhibitor of poly ADP-ribose polymerase (PARP) developed as a monotherapy as well as for combination with chemotherapy, ionizing radiation and other anti-cancer agents including novel agents and immunotherapy. The approved tradename for olaparib is LYNPARZA. Since 2012, the tablet formulation was designed to deliver the therapeutic dose of olaparib in fewer dose units than the capsule.

Active Ingredients and pharmacological class:

Chemical Name: 4-[(3-{[4-(cyclopropylcarbonyl)piperazin-1-yl]carbonyl}-4-fluorophenyl)methyl]phthalazin-1(2H)-one.

Dose formulation and storage:

Olaparib is presented for po administration as a green, film-coated tablet containing 25 mg, 100 mg or 150 mg of drug substance. The 100 mg strength is also available as a yellow, film-coated tablet. Olaparib tablets are supplied in high-density polyethylene (HDPE) bottles containing desiccant.. Bottles are secured with a child-resistant closure; induction-sealed membranes provide tamper evidence.

The planned dose of olaparib for this study is at a dose of 300 mg orally twice daily (bid). Olaparib is available as a green film-coated tablet containing 150 mg or 100 mg. The planned dose of 300 mg bid will be made up of two x 150 mg tablets bid with 100 mg tablets used to manage dose reductions.

Olaparib will be supplied by Merck. Co. LTD. through their collaboration with AstraZeneca.

Refer to the Investigator's Brochure for Preclinical and Clinical data.

6.0 CRITERIA FOR PARTICIPANT ELIGIBILITY

6.1 Participant Inclusion Criteria

This is an on-platinum maintenance trial either in a first-line or second-line setting.
 Participants must have either stable disease or responding disease on current first-line or second-line platinum treatment for metastatic disease.

0

POLAR: a phase 2 trial for pembrolizumab and olaparib maintenance for metastatic PDAC and HRD and/or Exceptional Response to Platinum – Ver. 5/3/2020

2. Male or female patients with cytologically or histologically confirmed metastatic pancreas adenocarcinoma or acinar cell carcinoma with homologous recombination gene alterations or platinum sensitivity as per following cohort inclusion criteria below.

Patients will be assigned to cohorts based on their genetic alterations and clinical response. Patient stratification to different Cohorts will be in the order of more canonical homologous recombination-gene (HR-gene) order. For example, patients who meet criteria for both A and B Cohorts, they will be assigned to Cohort A, not B. Cohorts will be defined as following by CLIA-approved NGS or MSK-IMPACT Part A or C:

- Cohort A: Patients with either pathogenic germline or somatic alterations of 3 core HR-genes
 (BRCA1/2, or PALB2) who have stable or responding disease on first-line or second-line platinum therapy in two consecutive imaging assessments over at least 4 months or 16 weeks are eligible for inclusion in Cohort A.
- Cohort B: Patients with either pathogenic somatic or germline non-core 15 HR-gene alterations (ATM, BAP1, BARD1, BLM, BRIP1, CHEK2, FAM175A, FANCA, FANCC, MUTYH, NBN, RAD50, RAD51, RAD51C, RTEL1) who have stable or responding disease on first-line or second-line platinum therapy in two consecutive imaging assessments over at least 4 months are eligible for inclusion in Cohort B.
- Cohort C: Patients without any of the above HR-gene alterations included in Cohort A and B who have platinum-sensitivity, which is defined as a partial response (PR) or complete response (CR) for the best overall response (BOR) during at least 6 months on platinumbased therapy. Variants of unknown significance of candidate HR-genes from Cohort A or B will be eligible for Cohort C if they meet the partial response to platinum criterion.
- Variants of unknown significance (VUS) or benign polymorphisms of above 17 HR-genes from Cohort A and B are considered non-pathogenic and will be excluded from cohort A or B. However, if the participant demonstrates platinum sensitivity, patient can be considered eligible for Cohort C.
- 3. A recurrence after curative surgery is eligible if the recurrence is > 6 months after the last date of adjuvant therapy and the participant has at least stable or responding disease on platinum therapy and meet the above genomic or platinum sensitivity criteria.
- Eastern Cooperative Oncology Group (ECOG) performance status 0-2 (Appendix 1: ECOG)
- 5. Patients must have normal organ and bone marrow function measured within 28 days prior to administration of study treatment as defined as below:
 - Absolute neutrophil count (ANC) ≥1500/µL
 - Hemoglobin ≥9.0 g/dL or ≥5.6 mmol/La
 - Platelets ≥100 000/µL

POLAR: a phase 2 trial for pembrolizumab and olaparib maintenance for metastatic PDAC and HRD and/or Exceptional Response to Platinum – Ver. 5/3/2020

•

2

- Total bilirubin ≤ 2 x ULN
- AST (SGOT) and ALT (SGPT) ≤2.5 × ULN (≤5 × ULN for if liver metastases)
- Creatinine ≤2 x ULN
- 6. Patients with measurable disease and/or non-measurable or no evidence of disease assessed at baseline by CT (or MRI where CT is contraindicated) are eligible.
- 7. Postmenopausal or evidence of non-childbearing status for women of childbearing potential: negative urine or serum pregnancy test. Postmenopausal is defined as:
 - Amenorrhoeic for 1 year or more following cessation of exogenous hormonal treatments
 - Luteinizing hormone (LH) and Follicle stimulating hormone (FSH) levels in the postmenopausal range for women under 50
 - Radiation-induced oophorectomy with last menses >1 year ago
 - Chemotherapy-induced menopause with >1-year interval since last menses
 - Surgical sterilization (bilateral oophorectomy or hysterectomy)

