13.0 CRITERIA FOR OUTCOME ASSESSMENT AND ENDPOINT EVALUABILITY

13.1. Tumor Measurements

Response Evaluation Criteria in Solid Tumors (RECIST) version 1.1 will be used to determine treatment response. Baseline tumor measurements will be performed prior to initiation of therapy. These measurements should be done according to iRECIST (see Appendix 2) ⁵⁴. An estimate of overall objective and subjective response will be made and recorded at the end of treatment at 8 weeks after the last infusion. Since it is expected that immune activity would lead to tumor flare, the restaging CT scans may be repeated 8 weeks later based on irRECIST and the designation of iCR, iPR, iSD, iUPD, or iCPD will be made at that time. Best overall response will be used.

- **13.1.2.** Disease control rate (DCR): DCR is defined as the percentage of patients who have achieved complete response, partial response, and stable disease to the study treatment.
- **13.1.3.** Overall response rate (ORR): ORR is defined as the percentage of patients who have achieved complete response and partial response to the study treatment.
- **13.1.4. Best Overall Response (BOR):** BOR is defined as the best response recorded from the start of the study treatment until the disease progression/recurrence.
- **13.1.5.** Durable response rate (DRR): DRR is defined as the percentage of patients who had achieved continued disease responses (CR and PR) for more than 6 months.
- **13.1.6.** Durable disease control rate (DDCR): DDCR is defined as the percentage of patients who had achieved continued disease controls (CR, PR, and SD) for more than 6 months from the time from the initiation of study treatment.
- **13.1.7. Additional Assessments.** All patients will have a baseline tumor marker assessment and testing of tumor markers at the designated follow-up time points. Changes in serial tumor marker measurements, in those patients who have baseline elevations, will be utilized as a surrogate marker of clinical response, stable disease or disease progression and reported as such.
- **13.1.8. Patients without residual disease:** For patients whose primary tumor or metastatic disease has been removed or successfully treated, respectively, prior to entry into this trial, progression free survival will be evaluated based on duration of relapse-free survival.
- **13.1.9. Progression free survival (PFS):** PFS is defined as the time from the initiation of study treatment to radiographic progression or death.

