13.2 Criteria for Study Endpoint Evaluability

- All patients who receive at least one dose of olaparib and pembrolizumab are considered to be evaluable for toxicity.
- All patients who receive at least olaparib for 14 days of 21-day course and one dose of pembrolizumab are considered to be evaluable for efficacy evaluation.

- Patients who enroll with a complete response on platinum-based treatment are evaluable and a radiographical disease recurrence by RECIST v 1.1 will be considered a progression.
- Patients who are screened eligible but subsequently withdraw from the study prior to receiving pembrolizumab with olaparib are considered inevaluable and will be replaced on the study.

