A two stage design will be employed only in Cohort A with co-primary endpoints ORR by iRECIST and 6-month PFS rate⁷ by RECIST v1.1. An initial cohort of 20 patients will be treated. If 14 or more patients are alive and progression free at the 6 months follow-up or if 6 or more objective responses are observed, an additional 13 patients will be accrued for a total of 33 patients. If 23 or more of the 33 patients are alive and progression free at 6 months from start of treatment or if 12 or more objective responses are observed, we can conclude that the regimen is sufficiently active to warrant further testing in this group of patients. We will also evaluate the progression-free survival from the consent date secondarily to the treatment start date (C1D1). We used the reference from historical data for these co-primary endpoints. 6-months PFS rate was 50% and ORR was 20% in singleagent olaparib study arm compared to placebo control arm in maintenance setting⁷. This design yields 81% power to detect a true 6-month PFS rate of 77% or more and it yields 81% power to detect a true ORR of at least 43%. It yields approximately 0.95 probability of a negative result if the true 6-month PFS rate is no more than 53% and the true ORR is no more than 20%. The type I error for the ORR endpoint is 0.02 and the type I error for the PFS endpoint is 0.028 and so the overall type I error of the composite design is bounded at 0.05 (the sum of the two type I error rates for PFS and RR) while the type II error rate for the composite design is 0.09 (each design has a type II error rate of 0.09). The probability of early termination was calculated as the product of the probability of early termination for the PFS endpoint (0.904) and the probability of early termination for the RR endpoint (0.804), resulting in a probability of early termination of 0.73 for the composite endpoint. These calculations assume that ORR and PFS are independent, , the type 1 error slightly decreases if ORR and PFS are positively correlated, which is very likely. The calculations also assume that the 6 month PFS endpoint is binary. Patients who are lost to follow up before their 6 months PFS

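### Cohort A keeps patients who cannot have a partial response in the ORR denominator, and the 81% ORR power holds only if 43% is the rate over all treated patients

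*Protocol*

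**What the plan says.** - **Eligibility.** Protocol section 6.1, item 6, admits "Patients with measurable disease and/or non-measurable or no evidence of disease assessed at baseline by CT" (or by MRI where CT is contraindicated).
- **Evaluability.** Section 13.2 states: "Patients who enroll with a complete response on platinum-based treatment are evaluable". The only outcome rule it gives for them is that radiographic recurrence counts as progression. The Primary Efficacy Dataset in section 14.1 is defined by drug exposure alone, with no condition on measurable disease.
- **Endpoint.** Section 13.1.3: "ORR is defined as the percentage of patients who have achieved complete response and partial response to the study treatment". Section 13.1.8 says how PFS is assessed when disease was removed or successfully treated before entry. There is no matching provision for ORR.
- **Decision rule for Cohort A (section 14.0).** "An initial cohort of 20 patients will be treated". On the ORR side, "if 6 or more objective responses are observed, an additional 13 patients will be accrued for a total of 33 patients"; at the end, the regimen is declared active "if 12 or more objective responses are observed". At both stages the 6-month PFS count (14 of 20, then 23 of 33) is an alternative route.
- **Design values.** The reference is that "ORR was 20% in singleagent olaparib study arm", and of the design the protocol says "it yields 81% power to detect a true ORR of at least 43" percent. ORR type I error is given as 0.02.

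**The concern.** The population, the denominator and the cut-offs do not fit together for one of the two co-primary endpoints. A patient with no disease, or already in complete response at entry, has nothing that can newly respond. A patient with only non-measurable disease cannot have a partial response and can count only through a complete response. Yet 6 of 20 and 12 of 33 are counted over all treated patients.

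Such patients are foreseeable. Everyone enters stable or responding on platinum, and the baseline-biopsy footnote to Table 9 anticipates patients in major partial or complete response with too little disease for several biopsies. Section 13.1.8 shows that the protocol saw the issue for PFS.

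At stake is the ORR route to a positive result. The protocol does not say whether 20% and 43% refer to all treated patients or to those who can respond, and the answer decides what the 81% means. The same dilution affects the ORR estimates in Cohorts B and C, and Cohort C selects patients by their response to platinum.

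**Working it through.** **Inputs.** From section 14.0: n1 = 20, ORR cut-off 6; n = 33, ORR cut-off 12; null ORR 20%, alternative 43%; PFS cut-offs 14/20 and 23/33, null 53%, alternative 77%. Assumed, because the protocol does not give it: a share f of Cohort A that cannot respond, varied from 5% to 20%.

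**Step 1: reproduce the plan.** With b(x; n, p) the binomial probability,

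P(ORR success) = Σ over x = 6 to 20 of b(x; 20, p) × P[Bin(13, p) ≥ max(0, 12 − x)].

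- p = 0.43: 0.809 (stated 81%).
- p = 0.20: 0.0201 (stated 0.02).
- Early termination on ORR at p = 0.20, P[Bin(20, 0.20) ≤ 5]: 0.804 (stated 0.804).

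The protocol's arithmetic is right when every patient responds independently at the stated rate.

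**Step 2: 43% read as the rate over all treated patients.** Power stays at 0.809. The rate needed among patients who can respond is 0.43/(1 − f): 45.3% at f = 5%, 47.8% at 10%, 50.6% at 15% and 53.8% at 20%.

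**Step 3: 43% read as the rate among patients who can respond, and 0 in the rest.** The overall rate is 0.43 × (1 − f), and the null rate becomes 0.20 × (1 − f). The formula of step 1 gives:

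| f | overall ORR | ORR power | ORR type I error |
|---|---|---|---|
| 0 | 0.430 | 0.81 | 0.0201 |
| 5% | 0.409 | 0.74 | 0.0136 |
| 10% | 0.387 | 0.65 | 0.0089 |
| 15% | 0.366 | 0.55 | 0.0056 |
| 20% | 0.344 | 0.45 | 0.0034 |

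The rule becomes conservative, not inflated.

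**Step 4: soften the zero rate.** If the affected patients reach complete response at an assumed 10%, the overall rate is 0.43 × (1 − f) + 0.10 × f. Power is then 0.754 at 5%, 0.691 at 10% and 0.546 at 20%.

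**Step 5: the full either-endpoint rule.** Continue if the ORR or PFS count is met at stage 1; succeed if either is met at 33. ORR and PFS are taken as independent, as the protocol does, and the PFS rate is held at the stated value.

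| f | 6-month PFS 77% | 6-month PFS 53% |
|---|---|---|
| 0 | 0.97 | 0.82 |
| 10% | 0.95 | 0.66 |
| 20% | 0.92 | 0.47 |

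**Step 6: one example of adapted cut-offs.** Suppose 17 of the first 20 and 28 of the 33 have measurable disease. With the present cut-offs of 6 and 12, ORR power at 43% among those 28 is 0.56. With cut-offs of 5/17 and 11/28 it is 0.71, type I error at 20% is 0.014, and null early termination on ORR is 0.76.

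**The case against.** The best defence is that nothing in the power statement is wrong. Section 13.1.3 defines ORR as a percentage of patients with no measurable-disease limit, and section 14.0 speaks of a true ORR of at least 43%. Read together, 43% is the rate over all treated patients, and step 1 confirms the 81%. A reader might infer that the protocol's power figure is simply false; the documents do not support that. The shortfall needs both the other reading of 43% and a share of patients that the protocol does not state. The biopsy footnote shows that low disease burden is expected but supports no percentage, since a major partial response may still be measurable.

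Other tempting readings also go too far:

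- *Every such patient is a certain ORR failure.* Patients with only non-measurable disease can still reach complete response (step 4).
- *Missing 6 of 20 stops Cohort A.* It stops only if the PFS count is missed as well, and patients without disease can count as PFS successes.
- *The observed ORR cannot be compared with the 20% reference.* The protocol does not give the denominator behind that figure, so this cannot be shown.
- *Power is lost in Cohorts B and C.* They are exploratory and carry no power claim; only their ORR estimates are diluted.

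The defence that PFS rescues the trial stands only in part. It holds when 6-month PFS reaches 77%. The ORR route matters most when PFS does not, and step 5 shows that the loss is then almost fully felt.

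**Conclusion.** The inconsistency stands: patients who cannot have a partial response are eligible, evaluable and counted in the ORR denominator, and only PFS is adapted for them. The 81% is correct on the all-treated reading, but it then carries an unstated requirement of 47.8% or 53.8% among patients who can respond when 10% or 20% cannot. On the other reading, with a zero rate in the rest, ORR power is 0.74, 0.65, 0.55 and 0.45 at assumed shares of 5%, 10%, 15% and 20%. The chance of a positive trial drops little if 6-month PFS is 77% and substantially if it is 53%, assuming independence.

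The silence also leaves open whether a complete response carried over from platinum counts, since section 13.1 uses best overall response. The wording of section 13.1.3, response to the study treatment, points against counting it, so an inflated type I error should not be inferred; an explicit rule would close the question.

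This should be fixed. It is a conditional loss on one of two routes to success, not an error in the stated calculation.

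**What to change.** 1. Define the ORR analysis set as patients with measurable disease at baseline, in all three cohorts. In Cohort A the others count toward 6-month PFS only.
2. State that a complete response already present at entry is not an ORR response.
3. State that 6/20, 12/33 and the 81% power hold only when all patients are measurable, and restate ORR power for the expected measurable share.
4. Pre-specify exact ORR cut-offs by number measurable at each stage. They should not rise as the number measurable falls, should keep ORR type I error at or below 0.02, and should be listed with their early-termination probability. The 5/17 then 11/28 pair in step 6 is one such entry.

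**Cost.** Protocol wording and a small table, with no extra patients. The stated ORR power will be lower (0.71 in the example), and a complete response in a patient with only non-measurable disease would no longer count toward ORR.
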